6.1.5 Pharmacodynamic Analysis Population

The PD analysis population is defined as all participants in the safety population who have evaluable baseline and at least 1 evaluable postbaseline PD measurement. Treatment assignment will be summarized by actual treatment.

	Confidentiality Statement	
This document	may not be duplicated, copied, altered or removed from company	

	Controlled Quality Management Document	
	Sponsor:	Pitant Therapeutics Inc.
	Protocol Number:	PLN-74809-PSC-203
STATISTICAL ANALYSIS PLAN		

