6.2.2 Body Mass Index

Body mass index (BMI) will be calculated as follows:

$$\text{BMI (kg/m}^2\text{)} = \text{Weight at Screening (kg)} / [\text{Height at Screening (m)}^2]$$

	Confidentiality Statement	
This document		may not be duplicated, copied, altered or removed from company

Controlled Quality Management Document

Sponsor: Pliant Therapeutics Inc.

Protocol Number: PLN-74809-PSC-203

STATISTICAL ANALYSIS PLAN**6.2.3 Baseline and Change from Baseline**

Baseline is defined as the last non-missing value before the participant receives the first dose of study drug. Change from baseline is defined as the difference between baseline and any post-baseline records.

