6.6 Early Termination Assessments

Unscheduled early termination assessments will not be summarized unless the early termination visit falls on a scheduled visit.

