6.7 Unscheduled Visits

Only scheduled post baseline values will be tabulated. Post baseline repeat / unscheduled assessments will not be summarized but will be listed in the relevant appendices to the CSR.

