6.18 Pharmacodynamic Analyses

Biomarker analyses will be presented by treatment group for the PD Analysis Population per Table 1.

Table 1. PSC Biomarkers

Biomarker	Timepoints (Parts 1 and 2)	Timepoints (Part 3)
PRO-C3 [REDACTED]	Baseline, Weeks 2, 4, 8, 12 and Week 16 (off-treatment)	Baseline, Weeks 2, 4, 8, 12, 24, EOT (variable weeks) and EOS (variable weeks)
ELF [REDACTED]	Baseline, Weeks 4 and 12	Baseline, Weeks 4, 12 and 24
[REDACTED]	[REDACTED]	[REDACTED]
[REDACTED]	[REDACTED]	[REDACTED]
[REDACTED]	[REDACTED]	[REDACTED]
ALP, [REDACTED]	Baseline, Weeks 2, 4, 8, 12 and Week 16 (off-treatment)	Baseline, Weeks 2, 4, 8, 12, 18, 24, 32, 40, 48 and 52 (off treatment)

Biomarker results obtained from plasma, or serum samples will be summarized using descriptive statistics by treatment group and visit for each parameter. Actual biomarker concentration at each visit, the absolute change from baseline and relative change (percentage change) from baseline will be presented. [REDACTED]

[REDACTED]

Confidentiality Statement

This document [REDACTED] may not be duplicated, copied, altered or removed from company [REDACTED] without prior approval [REDACTED]

Controlled Quality Management Document

Sponsor:

Pliant Therapeutics Inc.

Protocol Number:

PLN-74809-PSC-203

STATISTICAL ANALYSIS PLAN

If provided, the result adjusted for dilution factor will be used in summaries and listings. Any samples hemolyzed, received ambient, or with a note indicating improper storage will be excluded from summaries and listed only. If a sample has been excluded, then the change from baseline for that sample will also not be calculated.

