6.19.3 Ultrasound-based Transient Elastography (FibroScan®)

Each participant will undergo an ultrasound-based transient elastography (FibroScan®) assessment at screening and Week 12 (Parts 1, 2, and 3) and at Week 24 (Part 3 only).

Confidentiality StatementThis document [REDACTED]
without prior approval [REDACTED]

may not be duplicated, copied, altered or removed from company [REDACTED].

Controlled Quality Management Document	
Sponsor:	Pliant Therapeutics Inc.
Protocol Number:	PLN-74809-PSC-203

STATISTICAL ANALYSIS PLAN

Descriptive statistics for observed values at baseline and postbaseline visits will be provided, along with the change from baseline to each postbaseline visit, tabulated by treatment group.

A comparison of each parameter (PLN-74809 vs. placebo) will be performed. P-values will be derived from t-tests.

[REDACTED]

[REDACTED]

Safety Analyses

Safety analyses will be presented by the treatment received for the Safety Population.

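### Sections 6.7 and 6.18 of the SAP together leave no readable route for a valid redraw to replace a spoiled scheduled biomarker sample, so a measured visit is treated as missing (minor)

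*SAP*

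**What the plan says.** Section 6.7 (Unscheduled Visits) has two sentences. The first is "Only scheduled post baseline values will be tabulated". The second deals with everything else: "Post baseline repeat / unscheduled assessments will not be summarized but will be listed in the relevant appendices to the CSR". Repeats are named alongside unscheduled values, and no exception follows.

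Section 6.18 (Pharmacodynamic Analyses) sets the sample-quality rule: "Any samples hemolyzed, received ambient, or with a note indicating improper storage will be excluded from summaries and listed only". It adds: "If a sample has been excluded, then the change from baseline for that sample will also not be calculated". The readable text does not mention a replacement sample.

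Two neighbouring rules are more permissive. Section 6.6 reads "Unscheduled early termination assessments will not be summarized unless the early termination visit falls on a scheduled visit", so an early termination value can be used when it coincides with a scheduled visit. Section 6.2.3 reads "Baseline is defined as the last non-missing value before the participant receives the first dose of study drug", which does not restrict baseline to scheduled values.

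The PD analysis population in Section 6.1.5 requires "evaluable baseline and at least 1 evaluable postbaseline PD measurement".

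**The concern.** Each rule is reasonable alone. Section 6.18 keeps spoiled samples out, and Section 6.7 keeps stray extra values from being mixed with visit values. The difficulty is the case where both apply. A scheduled sample fails, the participant is still in the study, and a valid sample is redrawn for that visit. Section 6.18 removes the first sample and Section 6.7 removes the second, which leaves the visit empty although it was measured.

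Precision would then be lost without a stated reason, in a trial with 21 participants per dose and, beyond Week 12, only the 7 placebo participants of Part 3. An unwritten replacement practice would be no better. If the question is settled after treatment codes are known, the choice between a failed sample, a redraw and a missing value is open to influence by the results.

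**Working it through.** **1. The two rules applied to one visit.** Suppose the scheduled sample is hemolyzed and a valid redraw is taken.

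- Scheduled sample: excluded under 6.18, with no change from baseline.
- Redraw: a post-baseline repeat, so listed only under 6.7.
- Values summarized at that visit: 0. Usable values in the database: 1.

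If the same thing happened before the first dose, the redraw would be the last non-missing pre-dose value and could serve as baseline under 6.2.3.

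**2. Reach to the models.** Section 6.7 speaks of tabulating and summarizing, not of modelling. Sections 6.18.1 and 6.18.2 report ANCOVA and MMRM results for the scheduled visits, and their readable text gives no separate rule for selecting records. That the redraw is also lost to the models is therefore an inference, not a stated rule. If the models were meant to use redraws while the tables do not, the two would rest on different data, and that too would need to be stated.

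**3. Inputs for size.** From Section 5, each of the 4 doses has 21 active and 7 placebo participants: 4 × (21 + 7) = 112, which matches the stated total. Pooled placebo is 4 × 7 = 28. Parts 1 and 2 treat for 12 weeks (Section 1), so at Week 24 only Part 3 contributes, with 21 active and 7 placebo. The SAP gives no rate of failed samples and no rate of redraws, so the counts lost below are assumptions.

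**4. Formula.** With equal variances, the standard error of a simple difference in means is proportional to √(1/a + 1/p), where a and p are the active and placebo counts.

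**5. Up to Week 12, one dose against pooled placebo.** Base: √(1/21 + 1/28) = 0.2887.

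- 1 active value lost (4.8%): √(1/20 + 1/28) = 0.2928, +1.4%.
- 2 lost (9.5%): √(1/19 + 1/28) = 0.2972, +3.0%.
- 3 lost (14.3%): √(1/18 + 1/28) = 0.3021, +4.7%.
- 4 lost (19.0%): √(1/17 + 1/28) = 0.3075, +6.5%.

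**6. Week 24, Part 3 only.** Base: √(1/21 + 1/7) = 0.4364. With one placebo value lost: √(1/21 + 1/6) = 0.4629, a ratio of 1.061, or about +6%.

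**7. How far this carries to the planned analyses.** The biomarkers legible in Table 1 (PRO-C3, ELF, ALP) each have at least two post-baseline visits. The MMRM draws information from a participant's other visits, so the loss there is smaller than these figures. The list of single-assessment biomarkers in 6.18.1 cannot be read, so it is not possible to say which markers, if any, would lose a participant entirely.

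**The case against.** The strongest reply is that restricting by-visit tables to scheduled values is ordinary practice and protects against picking among repeats. That stands, and the proposed rule preserves it: a valid scheduled value always takes precedence.

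Second, much of the SAP is redacted, including a long block ahead of Section 6.6, text in 6.18 just before the exclusion rule, and the model details. A visit-assignment or replacement rule could be there. This also stands. It limits the claim to the readable text, although Section 6.7 is categorical and points to no exception elsewhere.

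Third, harm requires both a failed scheduled sample and a valid redraw. Nothing readable says that failed biomarker samples are redrawn. Where they are not, the visit is missing anyway and this rule costs nothing. This stands and is why no expected loss is claimed.

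Fourth, the contrast with baseline is not a contradiction, because a last-pre-dose rule and a by-visit rule serve different purposes. That is fair. The contrast shows only that the SAP accepts an unscheduled value in one place.

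Two stronger readings are tempting. A reader might infer that Section 6.7 expressly bars repeats from every analysis, but its wording covers tabulation and summary only. A reader might also infer that the same two-rule mechanism covers MR imaging and FibroScan. It does not: the 6.18 exclusion concerns samples, and no readable rule in 6.19.1 or 6.19.3 excludes a non-evaluable scan. Section 6.7 alone would keep a repeat scan out of the tables, which is a weaker point.

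**Conclusion.** The point holds on the readable text. Taken together, 6.7 and 6.18 drop a valid redraw of a spoiled plasma or serum sample from the by-visit summaries and, by inference, from the ANCOVA or MMRM. This is a stated rule that gives a worse result than a readily available alternative.

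The size is unknown and probably small. The figures of 1.4% to 6.5%, and about 6% at Week 24, assume equal variances, a simple two-group difference and the stated counts of lost values. They do not estimate what will happen in this trial. The affected endpoints are exploratory or additional (Sections 3.4 and 3.5), the primary endpoint is TEAE incidence, and the sample size was set empirically, so no power claim is affected. Severity: minor.

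**What to change.** Add to Section 6.7:

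> If the scheduled post-baseline sample for a visit is excluded under Section 6.18, the first valid repeat collected for that same scheduled visit, in the same treatment status (on or off study drug), is used as that visit's value in the summaries and models. Where a valid scheduled value exists, it is used and repeats are listed only.

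Assign replacements before unblinding of the Part concerned and flag them in the listings. If the unblinding for the Part 1/2 interim analysis has already taken place, Section 6 of the SAP provides for an addendum. If a redacted section already contains such a rule, a cross-reference from 6.7 is enough.

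The same sentence may be extended to a repeat MR or FibroScan examination when the scheduled one gave no evaluable result.

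The cost is one or two sentences and a small programming step, with no new samples or visits. The downside is that a few values will lie some days off the nominal visit date.

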6.8 Conventions

6.8.1 Medical Coding

Adverse events and medical history will be coded using the Medical Dictionary for Regulatory Activities (MedDRA) [REDACTED]. Conditions will be assigned to a system organ class and preferred term based on the Investigator-reported verbatim term.

Any medications taken (other than study drug) will be coded using the World Health Organization Drug Dictionary (WHO Drug) [REDACTED] Version. Medications (both prior and concomitant) will be assigned to an Anatomical Therapeutic Chemical (ATC) Level 4 drug classification and preferred name based on the medication name reported on the eCRF.

6.8.2 Data Handling

All clinical data programming will be performed using SAS® statistical software package [REDACTED] and based on Clinical Data Interchange Standards Consortium (CDISC) data standards.

Controlled Quality Management Document

Sponsor: Pliant Therapeutics Inc.

Protocol Number: PLN-74809-PSC-203

STATISTICAL ANALYSIS PLAN**Confidentiality Statement**

This document [REDACTED] may not be duplicated, copied, altered or removed from company
without prior approval [REDACTED].

Controlled Quality Management Document	
Sponsor:	Pliant Therapeutics Inc.
Protocol Number:	PLN-74809-PSC-203
STATISTICAL ANALYSIS PLAN	

6.8.3 Summary Statistics

Continuous variables will be summarized using an 8-point summary, the number of non-missing observations, mean, standard deviation, median, interquartile range (Q1, Q3), minimum (min), and maximum (max).

PK concentration data will be summarized using a 11-point summary, the number of non-missing observations (n), arithmetic mean (mean), standard deviation (SD), geometric mean, median, interquartile range (Q1, Q3), minimum (min), maximum (max), coefficient of variation (CV%) and geometric CV%

Categorical variables will be summarized by presenting the frequency and percent. Percentages will be based on the number of non-missing observations or the count in the participant population, unless otherwise specified. For each variable, all categories will be shown. Zero frequencies (but not the percent) within a category will be presented.

Incidence of AEs, medical history, and concomitant medications will be reported at the participant level. Participants can only be counted once within each preferred term and system organ class under the highest severity and relationship to study drug. Percentages will be calculated using the number of participants in the treatment group for the Safety Population.

6.8.4 Decimal Places

For summary statistics, n will be reported as a whole number. Means, medians, and percentiles will be displayed to 1 more decimal place than the data, dispersion statistics (eg, standard deviation) will have 2 more decimal places, and the minimum and maximum will be displayed to the same number of decimal places as reported in the raw data.

Where appropriate, less decimal places may be used on a case-by-case basis as denoted in the table shells.

Percentages will be displayed with 1 decimal place. All data presented in the individual participant listings will be as recorded on the eCRF.

6.8.5 Data Displays

All TFLs will be generated as individual Rich Text Format (.rtf) files using SAS [REDACTED]. Data summaries and graphical analyses will be reported within Section 14 of the CSR and individual participant data listings within Appendix 16.2 of the CSR.

Confidentiality Statement	
This document [REDACTED] without prior approval [REDACTED]	may not be duplicated, copied, altered or removed from company [REDACTED]

	Controlled Quality Management Document	
	Sponsor:	Pliant Therapeutics Inc.
	Protocol Number:	PLN-74809-PSC-203

STATISTICAL ANALYSIS PLAN

Participant disposition, baseline characteristics, and demographics, will be presented by treatment group (including all PLN-74809) and overall. Other summaries will be presented by treatment group (including all PLN-74809) only.

Treatment group labels will be displayed as follows:

PLN-74809 40 mg (N=XX)	PLN-74809 80 mg (N=XX)	PLN-74809 160 mg (N=XX)	PLN-74809 320 mg (N=XX)	All PLN-74809 (N=XX)	Placebo (N=XX)
------------------------------	------------------------------	-------------------------------	-------------------------------	----------------------------	-------------------

Listings will be sorted in the following order, study part (Parts 1, 2, and 3), treatment group, participant number, parameter, and visit unless otherwise stated. All data for randomized participants will be listed.

6.9 Participant Disposition

The overall total of participants in the screened population will be summarized. The number of participants randomized will be summarized by treatment group and overall.

Participant disposition will be summarized by treatment group and overall for the safety population, as follows:

- The number of participants in each analysis population (Safety, PK, and PD).
- The number of participants who complete the study drug.
- The number of participants who discontinue the study drug and the reason for discontinuation of study drug.
- The number of participants who complete the study.
- The number of participants who withdraw from the study and the reason for withdrawal.

6.10 Protocol Deviations

Number of participants with protocol deviations will be presented by treatment group, category, and classification (critical, major, minor, and total) as well as listed. Percentages will be based on number of participants in the safety population.

6.11 Pooled Placebo

Participants in the placebo group will be pooled across study Parts for summaries and comparison to PLN-74809 treatment groups.

--	--

Controlled Quality Management Document

Sponsor:	Pliant Therapeutics Inc.
----------	--------------------------

Protocol Number:	PLN-74809-PSC-203
------------------	-------------------

STATISTICAL ANALYSIS PLAN**Confidentiality Statement**

This document [REDACTED] may not be duplicated, copied, altered or removed from company [REDACTED] without prior approval [REDACTED].

Controlled Quality Management Document

Sponsor:

Pliant Therapeutics Inc.

Protocol Number:

PLN-74809-PSC-203

STATISTICAL ANALYSIS PLAN**6.12 Baseline and Clinical Characteristics**

Baseline summaries will be presented by treatment group (PLN-74809 dose (40, 80, 160 or 320 mg, All PLN-74809) or Placebo) and overall (PLN-74809 dose and Placebo) for the following variables based on the safety population:

Demographic Data

- Age at informed consent (years)
- Sex
- Ethnicity
- Race, where more than 1 race is selected the participant will be presented under the 'Multiple races' category in the summary but each selected race will be displayed in the listing.

Baseline Characteristics

- Weight at Screening (kg)
- Height at Screening (cm)
- BMI at Screening (kg/m²)
- Fertility status (childbearing potential, postmenopausal, surgically sterile)

Clinical Characteristics

- Duration since diagnosis at baseline (defined as the number of months from start date of first date reported for medical history preferred term "Cholangitis sclerosing" to first dose)
- Use of UDCA (Yes/no)
- Duration of UDCA usage at baseline (defined as the number of months from start date of UDCA to first dose)
- Partial Mayo Score for IBD (for participants with IBD ongoing at screening)

■ [REDACTED]

6.13 Medical History

Separate tabulations of prior and ongoing conditions at screening will be presented by treatment group and overall for the safety population. All reported medical history data will be listed. Nonpharmacological procedures will be provided as a separate listing.

Confidentiality Statement

This document [REDACTED]
without prior approval

[REDACTED] may not be duplicated, copied, altered or removed from company [REDACTED]

Controlled Quality Management Document

Sponsor: Pliant Therapeutics Inc.

Protocol Number: PLN-74809-PSC-203

STATISTICAL ANALYSIS PLAN**6.14 Prior and Concomitant Medications**

Prior medications are defined as any medications taken prior to the first dose of study drug but stopping before the date of the first dose of study drug.

Concomitant medications are defined as medications taken on or after the date of the first dose of study drug or medications that were taken before the first dose of study drug and stopped after the first dose of study drug.

Prior and concomitant medications will be presented by ATC Level 4 classification and preferred name for each treatment group in the safety population.

All reported medications will be listed.

6.15 Exposure to Study Drug

Duration of exposure (in days) will be summarized by treatment group for the safety population.

6.16 Study Drug Compliance

Compliance (%) will be calculated for each participant and summarized by treatment group and overall. All compliance and study drug accountability data will be listed.

6.17 Pharmacokinetic Analyses

Blood samples for determination of plasma concentrations of PLN-74809 will be obtained
[REDACTED]
after administration of study drug [REDACTED]

Concentration data will be obtained for PLN-74809 [REDACTED]

PLN-74809 concentration data [REDACTED] will be summarized by dose level and visit at each scheduled sample time (nominal time) using descriptive statistics. Line plots will also be provided showing mean (SD) by visit. [REDACTED]

[REDACTED] Concentrations that are below the limit of quantification (BLQ) will be set to 0 for summary statistics. BLQ concentrations will be retained as BLQ in listings. The data will be reported to 3 significant figures.

Confidentiality Statement

This document [REDACTED] may not be duplicated, copied, altered or removed from company [REDACTED]
without prior approval [REDACTED]

Controlled Quality Management Document

Sponsor:

Pliant Therapeutics Inc.

Protocol Number:

PLN-74809-PSC-203

STATISTICAL ANALYSIS PLAN

Individual PLN-74809 concentration data [REDACTED]

[REDACTED] will be provided in listings. Data may be pooled with data from other studies for population PK and reported outside of the clinical study report.

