3.3 Secondary Pharmacokinetic Endpoints

The secondary PK endpoints are plasma PLN-74809 concentrations [REDACTED] at each sampling time point.

		Confidentiality Statement
This document [REDACTED]		may not be duplicated, copied, altered or removed from company [REDACTED]

Controlled Quality Management Document

Sponsor:

Pliant Therapeutics Inc.

Protocol Number:

PLN-74809-PSC-203

STATISTICAL ANALYSIS PLAN

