5 RANDOMIZATION

For each planned PLN-74809 dose in each Part of the study, n=21 subjects will be randomized to PLN-74809 and n=7 participants will be randomized to placebo for a total of n=28 and in total, N=112 for 4 PLN-74809 doses (40, 80, 160 and 320 mg).

Approximately 112 participants may be enrolled in this study (28 participants in Part 1, 56 participants in Part 2, and 28 participants in Part 3).

Part 1: 28 eligible participants will be randomized in a 3:1 ratio (40 mg PLN-74809:placebo).

Part 2: 28 eligible participants per cohort (56 in total) will be randomized in a 3:1 ratio (PLN-74809:placebo). PLN-74809 doses administered in each cohort will be 80 mg or 160 mg.

Part 3: 28 eligible participants will be randomized in a 3:1 ratio (320 mg PLN-74809:placebo).

Randomization will be stratified by use of ursodeoxycholic acid (UDCA) (yes/no).

Confidentiality Statement

This document [REDACTED]
without prior approval [REDACTED]

may not be duplicated, copied, altered or removed from company [REDACTED].

	Controlled Quality Management Document	
	Sponsor:	Pliant Therapeutics Inc.
	Protocol Number:	PLN-74809-PSC-203
STATISTICAL ANALYSIS PLAN		

Participants will be centrally randomized at the baseline visit using an interactive response technology (IRT) system, according to a computer-generated randomization scheme. Randomization will occur immediately prior to the first dose (Day 1).

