6.1.4 Pharmacokinetic Concentration Population

The PK concentration population is defined as all participants in the safety population who have any valid PLN-74809 concentration data not including BLQ values. Treatment assignment will be summarized by actual treatment.

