**6.2.8 Inexact Values**

In the case where a variable is recorded as “> x”, “≥ x”, “< x” or “≤ x”, a value of x will be taken for analysis purposes. All data will be presented as is for listing purposes.

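### Setting BLQ concentrations to 0 makes the geometric mean 0 and the geometric CV% undefined in any PK summary cell that contains a BLQ value (minor)

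*SAP*

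**What the plan says.** SAP section 3.3 makes concentrations a secondary endpoint: "The secondary PK endpoints are plasma PLN-74809 concentrations", at each sampling time.

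Section 6.8.3 fixes how they are summarized: "PK concentration data will be summarized using a 11-point summary". After n, the arithmetic mean and the SD, the list continues with "geometric mean, median, interquartile range (Q1, Q3), minimum (min), maximum (max), coefficient of variation (CV%) and geometric CV"%.

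Section 6.17 defines the summary cell, in that concentrations "will be summarized by dose level and visit at each scheduled sample time (nominal time) using descriptive statistics". It then gives the rule for low values: "Concentrations that are below the limit of quantification (BLQ) will be set to 0 for summary statistics". The same section keeps BLQ as BLQ in the listings and plots the arithmetic mean with its SD. Some text directly before the BLQ sentence is redacted.

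Two other visible provisions deal with values below a limit:

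- Section 6.1.4 defines the PK concentration population as "all participants in the safety population who have any valid PLN-74809 concentration data not including BLQ values".
- Section 6.2.8 covers inexact values in general. For a result recorded as below x, "a value of x will be taken for analysis purposes".

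**The concern.** The zero rule is written for summary statistics as a whole, and two of the statistics it has to feed are computed on the log scale. A single zero removes the information from both. A geometric mean of 0 in a table would misdescribe exposure at that dose and time, and the geometric CV% could not be filled in at all.

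Whoever programs the table must then print the 0 or choose an unplanned workaround, and the available workarounds give different answers. What is at stake is the readability of descriptive tables for a secondary endpoint. No hypothesis test is involved.

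**Working it through.** The plan states no figure to reproduce. The check applies its rules literally.

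**Inputs from the SAP**
- BLQ = 0 in summaries (section 6.17).
- 11 statistics (section 6.8.3): n, mean, SD, geometric mean, median, Q1, Q3, minimum, maximum, CV%, geometric CV%. Two use logs and nine do not.
- Cell = dose level × visit × nominal time (section 6.17).
- Largest cell: 21, since "n=21 subjects will be randomized to PLN-74809" for each dose (section 5).

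**Step 1: do zeros reach the cells?** Section 6.1.4 works at participant level. It excludes a participant with no quantifiable concentration, but a participant with at least one stays in, together with any single BLQ samples. Section 6.2.8 would put the limit x in place of the value. However, it is general, and section 6.17 is specific to BLQ concentrations and says 0. Zeros therefore enter wherever a retained participant has a BLQ sample.

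**Step 2: formulas with one zero**
- Geometric mean = (product of x)^(1/n). One factor of 0 gives 0.
- Geometric CV% = 100 × sqrt(exp(var(ln x)) − 1). ln 0 does not exist, so this is undefined.
- The result is the same with 1, 5, 10 or 20 BLQ of 21 (4.8%, 23.8%, 47.6%, 95.2%). With no BLQ value there is no effect.
- In an all-BLQ cell, arithmetic CV% = 100 × SD / mean = 100 × 0/0, also undefined.

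**Step 3: illustration.** These data are assumed and do not come from the SAP: 21 lognormal quantiles with median 100 and log-SD 0.5, the lowest k being BLQ.

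| k BLQ | Mean (SD), BLQ = 0 | CV%, BLQ = 0 | Median, BLQ = 0 | Geometric mean / CV%, BLQ = 0 | Geometric mean / CV%, quantifiable only |
|---|---|---|---|---|---|
| 0 | 112.4 (57.2) | 50.9 | 100.0 | 100.0 / 52.9 | 100.0 / 52.9 |
| 1 | 110.6 (60.1) | 54.4 | 100.0 | 0 / undefined | 105.1 / 47.8 |
| 3 | 105.7 (66.8) | 63.3 | 100.0 | 0 / undefined | 113.7 / 42.1 |
| 10 | 79.7 (85.8) | 107.6 | 100.0 | 0 / undefined | 145.5 / 31.1 |

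The arithmetic statistics remain computable but move. Substituting half the quantification limit for one BLQ value, with the limit assumed to be 0.1 to 5, gives a geometric mean of 73.0 to 87.9 and a geometric CV of 433% to 117%. The choice of workaround therefore matters.

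**Step 4: how often?** The document shows no BLQ rate. If samples are independent with BLQ probability p, a cell of 21 contains at least one BLQ value with probability 1 − (1 − p)^21. For p = 1%, 2%, 5% and 10% (assumed) this is 19%, 35%, 66% and 89%.

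**The case against.** The strongest reply is redaction. Text is blacked out immediately before the BLQ sentence, and section 9, on changes to planned analyses, shows no content. An exception for the geometric statistics could stand in either place. That possibility remains and makes the point conditional. It does not remove it, because the BLQ sentence is complete as it stands and the visible text after it gives no exception.

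Second, no affected cell can be shown. No quantification limit, BLQ rate or pre-dose sample is visible, and the population in section 6.1.4 already removes participants whose every value is BLQ. This is right as to frequency. It does not cure the rule, since single BLQ samples from retained participants still count.

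Third, the consequence is small. The tables are descriptive, the line plots use the arithmetic mean and SD, and the listings keep BLQ. This stands, and it sets the severity.

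Three stronger readings are tempting and are not supported:

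- A reader might infer that the PK summaries as a whole are unusable. They are not: the arithmetic and order statistics can still be computed, apart from the CV% in an all-BLQ cell.
- A reader might infer that sections 6.2.8 and 6.17 contradict each other. The specific BLQ rule governs, so there is no real conflict.
- A reader might infer that the plan has no rule for the geometric statistics. The redactions do not allow that statement. What can be said is that the visible rule gives an unusable result.

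**Conclusion.** The point holds as a minor defect of the visible text. In any cell with at least one BLQ value, 2 of the 11 planned statistics carry no usable information. In an all-BLQ cell the arithmetic CV% fails as well, making 3 of 11. The other statistics stay computable, which is not the same as unaffected, because zeros pull down the mean and minimum and can move the SD and quartiles.

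The result in an affected cell is exact and needs no assumption about the concentrations. The share of affected cells is unknown and could be anything from none to all; the percentages in the last step of the working rest on assumed BLQ rates. The conclusion also assumes that no redacted sentence supplies an exception. No visible test or decision depends on these statistics.

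**What to change.** Amend section 6.17 as follows:

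- Limit BLQ = 0 to n, arithmetic mean, SD, CV%, median, quartiles, minimum and maximum.
- Compute the geometric mean and geometric CV% from quantifiable values only, and show in each cell the number quantifiable and the number BLQ.
- Show 'not calculated' for the geometric statistics when there are too few quantifiable values, with the minimum number stated in advance, and for the arithmetic CV% when all values are BLQ.

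The cost is a short wording change and two counts in the PK table. If the data for the Part 1/2 interim analysis have already been unblinded, section 6 routes the change to an SAP addendum.

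The downside is that the geometric statistics then describe quantifiable samples only. They run high, and their spread runs low. In the illustration, the geometric mean rises from 100.0 to 113.7 with 3 BLQ of 21 and to 145.5 with 10, so it must be read with the BLQ count. If the redacted text already states such a rule, nothing needs to change.
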